10.6.3 Pharmacokinetic Analysis

The pharmacokinetic analysis will be conducted on the PK Population.

The CSF concentrations will be summarized using descriptive statistics and the RO7234292 half-life in CSF will be calculated, if possible.

Other PK parameters, as appropriate, may be determined or calculated at the discretion of the PK scientist. Additional details regarding the PK analysis will be described in the SAP.

10.6.4 Pharmacodynamic and Clinical Analysis

The analyses of pharmacodynamic and clinical endpoints will be conducted on the Per Protocol and Safety Populations.

These evaluations will be summarized using descriptive statistics by study visit and regimen. Change and percent change from baseline over time will be summarized as appropriate. Comparison between regimens may be performed.

Additional analyses to investigate the relationship between the disease burden score (i.e., calculated from patients' age and CAG repeat length, CAG $_n$, using the formula: (CAG $_n$ - 35.5) x age) and these endpoints may be performed as where deemed appropriate.

Details will be described in the SAP.

11. INVESTIGATOR'S REGULATORY OBLIGATIONS

11.1 Informed Consent

Huntington's disease is known to cause behavioral changes, and patients who wish to participate in this study may have disturbances in judgment and decision-making (Walker 2007). During the consent process, the Investigator must carefully evaluate the patient's capacity to consent. To facilitate this evaluation, the Evaluation to Sign Consent questionnaire will be administered (DeRenzo et al. 1998). In cases where the Investigator is uncertain as to whether the patient possesses capacity to consent, the patient should be referred to an independent expert for further assessment of capacity. A prospective patient's consent will be sought only if

Protocol

he or she demonstrates during the consent process an adequate level of understanding of the study, its requirements and its risks.

The written informed consent document should be prepared in the language(s) of the potential patient population, based on an English version provided by the Sponsor or designee.

Before a patient's participation in the trial, the Investigator is responsible for obtaining written informed consent from the patient after adequate explanation of the aims, methods, anticipated benefits, and potential hazards of the study and before any protocol-specific screening procedures or RO7234292 is administered. The patient must be given sufficient time to consider whether to participate in the study. Consent for genetic testing within the study will be obtained separately from consent for participation in the other aspects of the study.

The acquisition of informed consent and the patient's agreement or refusal to notify his/her primary care physician should be documented in the patient's medical records and the informed consent form should be signed and personally dated by the patient and by the person who conducted the informed consent discussion (not necessarily an Investigator). The original signed informed consent form should be retained in the Study Master File and in any other locations required by institutional policy, and a copy of the signed consent form should be provided to the patient.

11.2 Ethical Conduct of the Study

The Guidelines of the World Medical Association Declaration of Helsinki dated October 2002 the applicable regulations and guidelines of current Good Clinical Practice (GCP) as well as the demands of national drug and data protection laws and other applicable regulatory requirements will be strictly followed.

11.3 Independent Ethics Committee/Institutional Review Board

A copy of the protocol, proposed informed consent/assent forms, other written patient information, and any proposed advertising material must be submitted to the IEC/IRB for written approval. A copy of the written approval of the protocol and informed consent form must be received by the Sponsor or designee before recruitment of patients into the Study and shipment of Study Drug. A copy of the written approval of any other items/materials that must be approved by the Study Center or IEC/IRB must also be received by the Sponsor or designee before recruitment of patients into the Study and shipment of Study Drug. The Investigator's Brochure must be submitted to the IEC/IRB for acknowledgement.

The Investigator must submit to and, where necessary, obtain approval from the IEC/IRB for all subsequent protocol amendments and changes to the informed consent document. The Investigator should notify the IEC/IRB of deviations from the protocol in accordance with ICH GCP Section 4.5.2. The Investigator should also notify the IEC/IRB of SAEs occurring at the Study Center and other AE reports received from the Sponsor or designee, in accordance with local procedures.

The Investigator will be responsible for obtaining annual IEC/IRB approval/renewal throughout the duration of the Study. Copies of the Investigator's reports, all IEC/IRB submissions and the IEC/IRB continuance of approval must be sent to the Sponsor or designee.

11.4 Patient Confidentiality

The Investigator must ensure that the patient's confidentiality is maintained. On the case report forms (CRFs) or other documents submitted to the Sponsor or designee, patients should be identified by initials, if permitted by local law, and a patient identification number only. Documents that are not for submission to the Sponsor or designee (e.g., signed informed consent forms) should be kept in strict confidence by the Investigator.

In compliance with Federal and local regulations/ICH GCP Guidelines, it is required that the Investigator and institution permit authorized representatives of the company, of the regulatory agency(s), and the IEC/IRB direct access to review the patient's original medical records for verification of study-related procedures and data. Direct access includes examining, analyzing, verifying, and reproducing any records and reports that are important to the evaluation of the study. The Investigator is obligated to inform and obtain the consent of the patient to permit named representatives to have access to his/her study-related records without violating the confidentiality of the patient.

Study data may be submitted to government or other health research databases or shared with researchers, government agencies, companies, or other groups that are not participating in this study. These data may be combined with or linked to other data and used for research purposes, to advance science and public health, or for analysis, development, and commercialization of products to treat and diagnose disease. Linking of data will be facilitated by the HDID number (see Section 6.3.2).

12. ADMINISTRATIVE AND LEGAL OBLIGATIONS

12.1 Protocol Amendments

Protocol amendments must be made only with the prior approval of the Sponsor or designee. Agreement from the Investigator must be obtained for all protocol amendments and amendments to the informed consent document. The regulatory authority and IEC/IRB must be informed of all amendments and give approval for any amendments likely to affect the safety of the patients or the conduct of the trial. The Investigator **must** send a copy of the approval letter from the IEC/IRB to the Sponsor or designee.

12.2 Study Termination

The Sponsor or designee reserves the right to terminate the study. The Investigator reserves the right to terminate their participation in the study, according to the terms of the site contract. The Investigator/Sponsor or designee should notify the IEC/IRB in writing of the trial's completion or early termination and send a copy of the notification to the Sponsor or designee.

12.3 Study Documentation and Storage

An electronic case report form (eCRF) utilizing an Electronic Data Capture application will be used for this study.

The Investigator should ensure that all appropriately qualified persons to whom he/she has delegated trial duties are recorded on a Sponsor-approved Delegation of Site Responsibilities Form.

Source documents are original documents, data, and records from which the patient's CRF data are obtained. These include but are not limited to hospital records, clinical and office charts, laboratory and pharmacy records, diaries, imaging, and correspondence. In this study, eCRFs may not be used as source documents.

The Investigator and Study Center staff are responsible for maintaining a comprehensive and centralized filing system of all study-related (essential) documentation in accordance with Section 8 of the ICH Guidelines (E6), suitable for inspection at any time by representatives from the Sponsor or designee and/or applicable regulatory authorities. Elements should include:

- Patient files containing completed CRFs, informed consents, and supporting copies of source documentation
- Study files containing the protocol with all amendments, Investigator's Brochure, copies
 of pre-study documentation and all correspondence to and from the IEC/IRB and the
 Sponsor or designee
- If drug supplies are maintained at the Study Center, proof of receipt, Study Drug Product
 Accountability Record, Return of Study Drug Product for Destruction, final Study Drug
 product reconciliation, and all drug-related correspondence

In addition, all original source documents supporting entries in the CRFs must be maintained and be readily available.

No study document should be destroyed without prior written agreement between the Sponsor or designee and the Investigator. Should the Investigator wish to assign the study records to another party or move them to another location, he/she must notify the Sponsor or designee.

12.4 Study Monitoring

The Sponsor representative and regulatory authority inspectors are responsible for contacting and visiting the Investigator for the purpose of inspecting the facilities and, upon request, inspecting the various records of the trial (e.g., CRFs and other pertinent data) provided that patient confidentiality is respected.

The Sponsor monitor or designee is responsible for inspecting the CRFs at regular intervals throughout the Study to verify adherence to the protocol; completeness, accuracy, and consistency of the data; and adherence to local regulations on the conduct of clinical research.

The monitor should have access to patient medical records and other study-related records needed to verify the entries on the CRFs.

The Investigator agrees to cooperate with the monitor to ensure that any problems detected in the course of these monitoring visits, including delays in completing CRFs, are resolved.

In accordance with ICH GCP and the Sponsor's audit plans, this Study may be selected for audit by representatives from the Sponsor's Clinical Quality Assurance Department (or designees). Inspection of Study Center facilities (e.g., pharmacy, drug storage areas, laboratories) and review of study-related records will occur to evaluate the trial conduct and compliance with the protocol, ICH GCP, and applicable regulatory requirements.

To ensure the quality of clinical data a clinical data management review will be performed on patient data received by the Sponsor or designee. During this review, patient data will be checked for consistency, omissions, and any apparent discrepancies. In addition, the data will be reviewed for adherence to the protocol and GCP. To resolve any questions arising from the clinical data management review process, data queries and/or Study Center notifications will be sent to the Study Center for completion and return to Sponsor or designee.

The Principal Investigator will sign and date the indicated places on the CRF. These signatures will indicate that the Principal Investigator inspected or reviewed the data on the CRF, the data queries, and the Study Center notifications, and agrees with the content.

12.5 Language

Case report forms must be completed in English. Generic names for concomitant medications should be recorded in English if possible, unless it is a combination drug, then record the trade name in English.

All written information and other material to be used by patients and investigative staff must use vocabulary and language that are clearly understood.

12.6 Compensation for Injury

The Sponsor maintains appropriate insurance coverage for clinical trials and will follow applicable local compensation laws. Patients will be treated and/or compensated for any study-related illness/injury in accordance with the information provided in the Compensation for Injury section of the Informed Consent document.

14. APPENDICES

Appendix A Schedule of Procedures

Appendix A Schedule of Procedures

Protocol

		Treatment Period (62 weeks)							Post- Treatment					
Study Period	Screen		Loading Period (6 weeks)			Maintenance Period ¹ (56 weeks)			Period** (12 weeks)					
Study Week	-4 to -1		•	I		2		5		6		7-62		74/ET
Study Day	-29 to -2	-1	1	2	3	8	28	29	30	36	57, 85, 421	58, 86, 422	64, 92, 428	519
Visit Window (days)*	-	*	0	*	*	±2	*	±5	*	±2	±5	*	±2	±21
Visit Type (cl = clinic, ph = phone)	cl	cl	cl	cl	ph	cl	cl	cl	ph	ph	cl	ph	ph	cl
Overnight Stay			x -	>										
Capacity to Consent Assessment and Informed Consent	Х													
Inclusion/Exclusion	X													
Medical History	X													
Vital Signs (BP, HR, RR, T)	X ²	Χ	Xa	Х		Х	Χ	Xa			Xa			Х
Orthostasis	X ²		Xb											Х
Physical and Neurological Exam ³	X ²	Χ	Xa	Xc		Χ	Χ	Xa			Xa			Х
Height	Х													
Body Weight	X ²	Х					Х				X			Х
C-SSRS⁴	X	Х	Xb	Х		Χ	Х	Xb			Xp			Х
Pregnancy Test⁵	X ²	Χ					Χ				Xp			Х
FSH	X ⁵													
Chemistry, Hematology, Urinalysis	X ⁶	Χ					Χ				Xb			Х
24-hour urine collection ⁷			x –	>										
Serum Biomarker Sample	X ⁶	Χ					Χ				Xp			Х
PT, INR, aPTT	X ⁶	Χ					Χ				Xp			Х
Archived Serum Sample ⁸	X^6	Х					Х				Xp			X

Protocol

Appendix A Schedule of Procedures Continued

		Treatment Period (62 weeks)								Post-				
Study Period	Screen	Loading Period (6 weeks)									Maintenance Period ¹ (56 weeks)			Treatment Period** (12 weeks)
Study Week	-4 to -1		•	1		2		5		6		7-62		74/ET
Study Day	-29 to -2	-1	1	2	3	8	28	29	30	36	57, 85, 421	58, 86, 422	64, 92, 428	519
Visit Window (days)*	-	*	0	*	*	±2	*	±5	*	±2	±5	*	±2	±21
Visit Type (cl = clinic, ph = phone)	cl	cl	cl	cl	ph	cl	cl	cl	ph	ph	cl	ph	ph	cl
Local PT, INR, aPTT, Platelets ⁹	Х	Х					Xb				X ^{b, 10}			Х
Thyroid Panel		Х					Х				Χþ			Х
Plasma Sampling for Immunogenicity Testing			Xb					Xp			Xp			Х
CSF Sample for PK/Safety/Biomarkers/Archive	X ¹¹		Xb					Xb			X ^{b, 10}			Х
ECG (12-lead; in Triplicate at Screening Visit Only)	X ₆	Х		Х							X ^{b, 14}			Х
qEEG	X ¹³										X ^{b, 14}			Х
Structural MRI	X ¹³										X ^{b, 14}			X ¹⁵
T2 flair, T2 star, T2 FSE/TSE MRI	X ¹³										X ^{b, 14}			X ¹⁵
RO7234292 Administration			Х					Х			X ¹⁰			
Adverse Events	Х	Х	Х	Х	Х	Х	Х	Χ	Х	Х	Х	Х	Х	Х
Concomitant Medications	Х	Х	Х	Х	Х	Х	Х	Х	Х	Х	Х	Х	Х	Х

Appendix A Schedule of Procedures Continued

Note: If not specifically labeled, "X" means anytime; ET = early termination

- * All visits windows are calculated relative Study Day 1, i.e., the date of first dose administration in this protocol. Visits with an asterisk (*) do not have a visit window and must be conducted on the exact day shown relative to the corresponding dosing day.
- ** Only patients who do not enter the open-label extension study (Study BN40955) will attend the Post-Treatment/End-of-Study visit.
- Patients are randomized to the Monthly Cohort or the Bimonthly Cohort. Patients in the Monthly Cohort receive *RO7234292* every 28 days during the Maintenance Period (14 doses in the Maintenance Period). Patients in the Bimonthly Cohort receive *RO7234292* every 56 days during the Maintenance Period (7 doses in the Maintenance Period). Study visits are shown below.

Monthly Cohort Study Visits during the Maintenance Period:

Study Weeks	Study Visit Day (Clinic Visit)	RO7234292 Dosing Visit?	Day After Dosing Visit (Phone Visit)	Seven Days After Dosing Visit (Phone Visit)
9/10	57	Y	58	64
13/14	85	Y	86	92
17/18	113	Y	114	120
21/22	141	Y	142	148
25/26	169	Y	170	176
29/30	197	Y	198	204
33/34	225	Y	226	232
37/38	253	Y	254	260
41/42	281	Y	282	288
45/46	309	Y	310	316
49/50	337	Y	338	344
53/54	365	Y	366	372
57/58	393	Y	394	400
61/62	421	Y	422	428

Appendix A Schedule of Procedures Continued

Bimonthly Cohort Study Visits during the Maintenance Period:

Study Weeks	Study Visit Day (Clinic Visit)	RO7234292 Dosing Visit?	Day After Dosing Visit (Phone Visit)	Seven Days After Dosing Visit (Phone Visit)
9/10	57	N		
13/14	85	Y	86	92
17/18	113	N		
21/22	141	Y	142	148
25/26	169	N		
29/30	197	Y	198	204
33/34	225	N		
37/38	253	Y	254	260
41/42	281	N		
45/46	309	Y	310	316
49/50	337	N		
53/54	365	Y	366	372
57/58	393	N		
61/62	421	Y	422	428

- 2 If the Screening visit is conducted on the same day as the patient's last visit in Study ISIS 443139-CS1 and this assessment was performed at that visit, this assessment does not need to be performed separately for Study BN40697 (i.e., the result from the patient's last visit in Study ISIS 443139-CS1 may serve as the Screening result for Study BN40697).
- 3 Full physical and neurological exam (including fundi) to be given at Screening and abbreviated physical (but full neurological) exam to be given during Treatment and Post-Treatment Periods as indicated to assess changes from Screening.
- The C-SSRS must be administered on the study days shown. It may also be administered at any time that the Investigator feels is necessary. At the Screening visit, the "Baseline/Screening" version of the C-SSRS must be administered, capturing patient's suicidal ideation and behavior over the prior year. In some cases, this collection period will overlap with the time period captured in Study ISIS 443139-CS1. If the Screening visit is conducted on the same day as the patient's last visit in Study ISIS 443139-CS1, then 2 forms must be completed: the "Since Last Visit" C-SSRS must be completed for Study ISIS 443139-CS1, and the "Baseline/Screening" C-SSRS much be completed for Study BN40697. In this situation, it is expected that a single interview with the patient will yield sufficient information to complete the C-SSRS forms for both studies.
- 5 Women who are not surgically sterile. Serum pregnancy at Screening visit (unless result from the patient's last visit in Study ISIS 443139-CS1 serves as the Screening result for Study BN40697); dipstick at post-screen visits.
- 6 If the Screening visit is conducted within 4 weeks of the patient's last visit in Study ISIS 443139-CS1 and this assessment was performed at that visit, this assessment does not need to be performed separately for Study BN40697 (i.e., the result from the patient's last visit in Study ISIS 443139-CS1 may serve as the Screening result for Study BN40697).
- 7 Ensure patient has voided bladder prior to start of *RO7234292* administration procedure. Start 24-hour urine collection immediately after *RO7234292* administration. Pool and record total urine volume.

- Stored at -80 °C for follow-up exploration of laboratory findings and/or AEs (e.g., measurement of cytokine and/or chemokine levels, measurement of additional markers of kidney function, measurement of antibodies) in this or subsequent clinical studies of *RO7234292*.
- 9 Local laboratory analysis of PT, INR, aPTT and platelets must be conducted and results reviewed prior to performing the lumbar puncture. Sample collection may occur at any time within 72 hours prior to the planned lumbar puncture.
- 10 Only at dosing visits. (See tables in Footnote 1.)
- 11 Screening CSF sample collected at least 2 weeks prior to Study Day 1. Screening sample is for Safety/Biomarkers/Archive only.

- 13 If the Screening visit is conducted within 3 months of the patient's last visit in Study ISIS 443139-CS1 and this assessment was performed at that visit, this assessment does not need to be performed separately for Study BN40697 (i.e., the result from the patient's last visit in Study ISIS 443139-CS1 may serve as the Screening result for Study BN40697).
- 14 This assessment is conducted on Study Days 85, 253 and 421 only. If necessary for ease of logistics, the assessment may be performed on a different calendar day than the dose administration (must be prior to the dose administration and within the required visit window).
- 15 If imaging is conducted after CSF collection, at least 1 day must elapse between the LP and the imaging session to avoid LP-related artifacts on the images.

Time (in reference to time of *RO7234292* administration):

- a Pre-dose; also 3 and 5 hours after administration of *RO7234292* (3- and 5-hour assessments are only performed if *RO7234292* has been administered)
- b Pre-dose at dosing visits (otherwise, at any time during the visit)
- c Approximately 24 hours after administration of RO7234292
- d Pre-dose, 0.5, 1, 2, 3, 4, 5, 6, 8 and 12 hours after administration of RO7234292
- e On Study Day 197: samples collected pre-dose and 0.5, 1, 2, 3, 4 and 5 hours after administration of *RO7234292*. On all other Study Days (57, 85, ... 421): 1 sample collected pre-dose (if *RO7234292* will be administered at the visit) or anytime during the visit (if *RO7234292* will not be administered at the visit)

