6.1.1 Screening Period (Week -4 to Week -1)

Written informed consent for the study will be obtained prior to the performance of any study-related procedures including screening procedures. During the Screening Period, inclusion/exclusion criteria will be evaluated to determine patient eligibility for the study. A single CSF sample will be collected during the Screening Period. At least 2 weeks must elapse between the screening CSF collection and Study Day 1. Abnormal laboratory screening results may be retested for review by the Study Medical Monitor for eligibility purposes.

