6.2.18 Collection of CSF

Patients will have CSF collected at the Screening Visit, prior to administration of each dose of RO7234292 and at the Post-Treatment Visit. At each collection, 20 mL of CSF fluid is to be collected for analyses. If there are difficulties in collecting 20 mL of CSF fluid, a minimum of 15 mL should be collected. A 24G atraumatic needle (Whitacre or other if approved by Sponsor prior to use) will be used. Depending on institutional guidelines, local anesthesia may be used for the procedure. Sedation may not be used. Spinal ultrasound may be used for the LP procedure, if deemed necessary, but is not required.

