8. TREATMENT OF PATIENTS

8.1 Study Drug Administration

RO7234292 dosing will occur at the Study Center. On administration days, each patient will undergo an LP procedure for collection of CSF (see Section 6.2.18) followed by a single IT bolus (1-3 minute) LP injection of RO7234292. A 24G atraumatic needle (Whitacre or other if approved by Sponsor prior to use) will be used, oriented with the opening rostral (toward the patient's head). The target site for needle insertion is the L3/L4 space but may be 1 segment above or 1-2 segments below this level, if needed. Depending on institutional guidelines, local anesthesia may be used for the LP procedure. Sedation may not be used. Spinal ultrasound may be used for the LP procedure, if deemed necessary, but is not required.

Please refer to the Study Drug Manual provided by the Sponsor or designee for more detailed instructions for dose preparation and administration, including volume of administration. These instructions must be followed for each dose administration.

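### The Screening MRI is the only scan with no stated order or gap relative to the lumbar puncture, and a reused scan up to about 120 days old can be the baseline for volume change reported by nominal visit

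*Combined protocol and SAP*

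**What the plan says.** **Scan and LP order.** Appendix A has two MRI rows, "Structural MRI" and the T2 sequences. Both carry Footnote 13 at Screening, superscript b with Footnote 14 in the Maintenance Period, and Footnote 15 at Day 519/early termination.

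- Footnote 15 applies when imaging follows CSF collection: "at least 1 day must elapse between the LP and the imaging session to avoid LP-related artifacts on the images".
- Footnote 14 limits the Maintenance scans to Days 85, 253 and 421. It allows another calendar day, but the scan "must be prior to the dose administration and within the required visit window".
- Section 8.1 makes CSF sampling and injection one session: on dosing days "each patient will undergo an LP procedure for collection of CSF", followed by the intrathecal injection.
- The note under Appendix A says that an X means any time, "If not specifically labeled".
- Section 6.2.18: "Patients will have CSF collected at the Screening Visit". The target volume is 20 mL, with a minimum of 15 mL.
- Section 6.1.1 times that LP only against first dose: "At least 2 weeks must elapse between the screening CSF collection and Study Day 1".

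**Age of the baseline scan.** Footnote 13 begins "If the Screening visit is conducted within 3 months of the" patient's last CS1 visit. If the assessment was done at that visit, its result may serve as the Screening result. This covers MRI and qEEG. Section 10.4 takes the last non-missing pre-dose value as baseline for these measures. Section 10.6.4 summarises by study visit and regimen, with change and percent change from baseline, and leaves details to a SAP whose text is not among the documents reviewed.

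**The concern.** These are two separate points, and they mostly affect different patients.

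**(a) New Screening scans.** The plan treats imaging soon after an LP as a source of artifact, and it guards every scan except the one from which later changes are computed. An artifact in a baseline scan carries into every later change for that patient.

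**(b) Reused CS1 scans.** MRI and qEEG are not repeated on Day -1 or Day 1, so a reused result becomes the baseline. Change at a given visit then covers a longer period for some patients than for others. If volumes change steadily, older baselines inflate mean within-regimen change and add between-patient noise. The extra time lies before dosing in this study. It is not necessarily untreated time, because CS1 patients received active drug or placebo.

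Structural MRI is a named secondary objective, and Section 2.4 gives imaging as part of the reason for the 56-week Maintenance Period. There is no placebo arm, and comparison between regimens is optional, so within-regimen change is the main imaging result.

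**Working it through.** **Day convention.** There is no Day 0. As a check, Day 421 to Day 519 is 98 days = 14 weeks, which matches the follow-up stated in Section 3.4.3.

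**(a) Overlap of windows at Screening**

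- MRI window (Appendix A): Day -29 to Day -2, 28 possible days.
- LP at least 14 days before Day 1, so Day -29 to Day -14: 16 possible days.
- All 16 LP days lie inside the MRI window, and no order or gap is stated. A scan on the day of the LP, after it, is allowed.

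| Scan | Protection in the visible text |
|---|---|
| Screening | None (Footnote 13 only) |
| Days 85, 253, 421 | Before the dose, hence before that visit's LP (Footnote 14, superscript b, Section 8.1) |
| Day 519 | At least 1 day after the LP if imaging follows it (Footnote 15) |

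**(b) Age of the baseline scan at Day 1**

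- New scan: 2 to 29 days.
- Oldest reused scan: 3 months taken as 91 days, plus Screening on Day -29, gives 91 + 29 = 120 days (118 to 121 if 3 calendar months are 89 to 92 days).

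**Baseline-to-visit interval** = (visit day - 1) + scan age at Day 1.

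| Visit | New scan, Day -2 | New scan, Day -29 | Oldest reused scan | Ratio, oldest to Day -2 | Full range with ±5-day window | Worst-case share before Day 1 |
|---|---|---|---|---|---|---|
| Day 85 | 84 + 2 = 86 | 113 | 84 + 120 = 204 | 204/86 = 2.37 | 81–209 | 120/204 = 59% |
| Day 253 | 252 + 2 = 254 | 281 | 252 + 120 = 372 | 372/254 = 1.46 | 249–377 | 120/372 = 32% |
| Day 421 | 420 + 2 = 422 | 449 | 420 + 120 = 540 | 540/422 = 1.28 | 417–545 | 120/540 = 22% |

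**Average case.** Assumptions: a constant rate of change, and reused scans uniformly 0 to 91 days older than new ones (mean 45.5 days). With a fraction f of patients reusing a scan, the overstatement of mean within-regimen change, relative to all-new baselines, is f × 45.5 / (midpoint of the new-scan interval). The midpoints are (86 + 113)/2 = 99.5, (254 + 281)/2 = 267.5 and (422 + 449)/2 = 435.5 days.

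| f (assumed) | Day 85 | Day 253 | Day 421 |
|---|---|---|---|
| 25% | 11.4% | 4.3% | 2.6% |
| 50% | 22.9% | 8.5% | 5.2% |
| 100% | 45.7% | 17.0% | 10.4% |

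The documents give neither f nor a rate of volume loss, so the effect can be stated relative to the change but not in volume units.

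**The case against.** The strongest case against has four parts.

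- **Removed text.** Section 6.2.8, where an MRI rule would naturally sit, has gaps, and Footnote 12 is absent. A general LP-to-scan rule may exist there. This stands as a limit on (a), which therefore rests on the visible schedule. In that schedule the Footnote 15 marker is legible at Day 519 and not present at Screening.
- **Unseen SAP.** Use of actual dates or annualised change is ordinary SAP content, and Section 10.6.4 defers details. This also stands. If the SAP already does this, confirming it closes the main analysis part of (b).
- **Unknown frequency.** Reuse requires that the last CS1 visit included the scan and that Screening came within 3 months of it. The number of such patients could be zero. The 2.4-fold ratio pairs two extremes, and at Day 421, the visit that matters most for a 56-week Maintenance Period, the average-case effect is 3% to 10%. All of this is correct.
- **Limited consequence.** Imaging is exploratory, the sample size was not set on it, and the analysis is mainly descriptive. Randomization follows completion of Screening (Section 4.2), so scan age is balanced between regimens in expectation. This too is correct. With at most 46 patients, chance imbalance remains possible.

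These points limit the size and priority of the concern. They do not supply the missing Screening rule or make the intervals equal.

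**Conclusion.** Both parts hold on the visible text.

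(a) The schedule permits a Screening MRI within a day after the Screening LP, which is the situation Footnote 15 is meant to avoid. How often this occurs, and how large the artifact would be, cannot be determined from the documents.

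(b) The permitted baseline-to-visit interval varies up to 2.4-fold at Day 85, 1.46-fold at Day 253 and 1.28-fold at Day 421. Under the stated assumptions, mean within-regimen change is overstated by about 11% to 46% at Day 85, 4% to 17% at Day 253 and 3% to 10% at Day 421 as reuse goes from 25% to 100%. It is not overstated at all if no scan is reused.

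The randomized comparison of Monthly with Bimonthly is not biased in expectation. This is a change worth making because it is cheap, and it does not threaten the trial's main conclusions. Confidence is medium, because Section 6.2.8 is incomplete and the SAP was not available.

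**What to change.** 1. **Appendix A.** Attach Footnote 15 to the Screening MRI cells, or require the Screening MRI before the Screening LP. For scans already taken, compute the LP-to-scan interval and run a sensitivity analysis excluding baselines obtained less than 1 day after an LP. If Section 6.2.8 in full already contains such a rule, a cross-reference is enough.
2. **Section 10.6.4 or the SAP.** Analyse MRI volume change from actual scan dates, as annualised change or with a mixed model in actual time. Report baseline scan age by regimen. Add a sensitivity analysis excluding reused CS1 scans, and the same exclusion for reused qEEGs.

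The cost is one footnote marker, some SAP wording, a slight scheduling constraint at Screening and a little more analysis. The exclusion analyses lose some of at most 46 patients. No additional scans are needed, and the analysis changes also work for data already collected.
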